## 1.7 Lack of Surgeon Consensus

The FLOW trial demonstrated a clear divide among orthopaedic surgeons regarding their choice to use the two most common antiseptic solutions during open fracture fixation surgery. Iodophor solutions were used in 54% of the surgeries performed, while 41% were performed using chlorhexidine solutions. The remaining surgeons either used both iodophor and chlorhexidine (4%), or alcohol with no iodophor or chlorhexidine (1%). Building upon the lack of consensus among orthopaedic surgeons participating in the FLOW trial, our research team conducted an internet-based survey and several interviews with orthopaedic surgeons to understand the reasons for the lack of consensus in the use of surgical preparation solutions. Similar to the observations of the FLOW trial, there was nearly an equal split between the use of iodophor and chlorhexidine solutions. More insight was gained in interviews with the surgeons. Three main drivers for surgeon decision-making were identified: 1) they continued to use the antiseptic solution shown to them during their surgical training, 2) they used the solution recommended by their hospital, or 3) they felt the tissue toxicity was less with their chosen solution. No surgeon could cite a clinical study that helped guide their decision, despite all surgeons indicating they believed the antiseptic solution was important for reducing their patient's risk of SSI. Limited consensus among surgeons reflects a lack of compelling evidence on the optimal approaches to surgical skin preparation, further vindicating the need for a large definitive trial.

The Aqueous-PREP trial, A Pragmatic Randomized trial Evaluating Pre-operative aqueous antiseptic skin solutions in open fractures, will address these gaps in the literature.

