## 4.6.5 Evaluation of Site Performance and Removal of Clinical Sites

After every two recruitment periods (approximately every four months), each site will be evaluated for continued participation in the trial. Sites with <90% of eligible patients receiving the allocated solution, differential adherence between study solutions, <95% follow-up of the primary outcome, <90% follow-up of the secondary outcome, incomplete data submission, or other threats to data quality or the validity of the study may be withdrawn from the trial. In the event a site is withdrawn, data collection will be completed for all enrolled participants and these data will be included in the final study analysis.

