#### 5.0 STATISTICAL PLAN

## 5.1 Sample Size Determination

The overall objective of the trial is to determine the most effective aqueous pre-operative antiseptic skin solution for use during open fracture management. This will be achieved by comparing the effectiveness of 10% povidone-iodine versus 4% CHG surgical skin preparations. The primary outcome is the occurrence of SSI, as per the adapted CDC criteria (**Table 3**). The secondary outcome is the occurrence of unplanned fracture-related reoperations within 12 months of injury. The sample size was calculated for the primary comparison between proportions of patients with SSI in each treatment group; however, it is expected that this estimate will also provide adequate power for the secondary outcome (unplanned fracture-related reoperation) because the baseline incidence (13%) and effect size for the reoperation outcome are expected to be similar to the SSI estimates.

Assuming an ITT principle for the analysis, the sample size was calculated based on a cluster crossover design with the cluster as the unit of randomization and the patient as the unit of analysis. For complex study designs, such as a cluster-randomized crossover trial, simple formulas to calculate sample size or power may not capture the expected variability from the observed data. Simulation methods were used to obtain empirical power calculations based on a feasible number of recruiting clusters and the expected number of open fracture patients. The simulation estimates are designed to detect a difference between the treatment groups, accounting for between hospital variability inherent to a cluster-crossover trial design. We have assumed that the povidone-iodine solution will achieve a 0.65 risk ratio for SSI with a 12.5% SSI baseline incidence. This represents approximately a 4% absolute risk reduction in SSI and reoperation. This effect was deemed more conservative than data reported by Swenson et al. and was consistent with feasible recruitment goals.

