Recent simulation data suggest that increasing the number of period crossovers can increase the statistical power of a given sample size. To ensure the most conservative sample size estimate, we have based our sample size assumptions using a single crossover, 2 period design. The initial power estimate assumed 10 recruiting clusters, a 10% loss to follow-up rate, and applying the between-cluster variance of 0.095 observed in the FLOW trial. Based on enrollment of a minimum of 1,540 open fracture patients, greater than 80% power would be achieved. Subsequent to the initial power calculations, the early trial experience demonstrated a need to increase the number

of clusters to obtain a feasible recruitment pace. As a result, a minimum of 12 clusters will enroll participants into Aqueous-PREP. The increase in clusters results in a marginal increase in power ( $\sim 2\%$ ).

**Table 5** below outlines the summary of the initial sample size assumptions that yield  $\geq 80\%$  power to detect difference between the treatments. These sample size estimates are rounded up to the nearest multiple of 20 to ensure balance among the clinical sites and two interventions.

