**Table 5: Sample Size Assumptions** 

Baseline SSI Risk	10% Povidone- Iodine Risk Ratio	10% Povidone- Iodine Odds Ratio	Sample Size	Sample Size Increased by 10%
10.0%	0.62	0.59	1600	1760
10.0%	0.65	0.63	1960	2100
10.0%	0.67	0.65	2200	2420
10.0%	0.70	0.68	2600	2860
12.5%	0.62	0.59	1300	1440
12.5%	0.65	0.62	1400	1540
12.5%	0.67	0.64	1600	1760
12.5%	0.70	0.67	1800	1980
14.0%	0.62	0.58	1200	1320
14.0%	0.65	0.61	1300	1440
14.0%	0.67	0.64	1500	1660
14.0%	0.70	0.67	1800	1980

**Note:** \*Between cluster ICC = 0.028; Between cluster variance\* = 0.095; Between period variance = 0; Number of clusters = 10; Number of periods = 2; Alpha = 0.05

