#### 5.2 Statistical Methods

## 5.2.1 Analysis Plan Overview

A detailed statistical analysis plan will be published prior to the completion of the trial. The analysis and reporting of the results will follow the CONSORT guidelines for reporting of both pragmatic trials and cluster-randomization trials. The process of patient enrollment and flow throughout the study will be summarized using a flow-diagram. Patient demographics and baseline outcome variables will be summarized using descriptive summary measures expressed as mean (standard deviation) or median (interquartile range) for continuous variables depending on the distribution, and number (percent) for categorical variables. An ITT principle will be adopted to analyze all outcomes and the unit of analysis will be the individual patients. Missing data will be assumed to be missing at random and will be handled with multiple imputation.

The primary analysis will compare the treatment groups on the SSI outcome and the secondary analysis will compare the unplanned fracture-related reoperation outcome. The secondary comparison will be conducted in accordance with best practice guidelines for secondary analyses. For all models, the results will be expressed as relative measure of effect (odds, risk, or hazard ratios) and corresponding two-sided 95% confidence intervals.

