- 4) As-treated analyses: The proportion of surgical procedures receiving the incorrect, non-allocated antiseptic solution will be reported. "As-treated" sensitivity analyses will be performed using the solution received as the independent variable. For participants that were treated in a single open fracture surgery, they will be analyzed using the antiseptic solution received. For participants who received multiple open fracture surgeries, two analyses will be performed. First, the antiseptic solution used in their last surgery prior to a study outcome event will define their study treatment. For the second analysis, the antiseptic solution received in the majority of their

fracture surgeries will define their study treatment. Participants who were treated with multiple open fracture management surgeries, but received equal exposure to both treatment solutions (e.g. one surgery with CHG and one surgery with iodine), will be analyzed within their originally allocated treatment group.

- 5) Co-intervention variability: Selective censoring of one or more clusters and / or treatment periods will be performed to further explore between-cluster and between-period variability identified in the primary and secondary outcome comparisons. These analyses will be used to explore the robustness of the study conclusions in the context of measured practice variations in co-interventions that differ between participating sites and / or evolve over the duration of the study recruitment. Results that are sensitive to the removal of a cluster(s) and / or period(s) will be reported, along with potential clinical hypotheses that are supported by the measured clinical practice variation.
- 6) Exploratory SSI definitions: The above analyses (See Section 5.2.2) will be repeated for the primary comparison using the FRI outcome and the CDC definition within 1 year of injury to determine if the study conclusions are sensitive to alternative definitions of SSI.

**Table 8** below shows a summary of the objectives, corresponding outcomes, hypotheses, and methods for each potential sensitivity analysis.

Table 8: Summary of Sensitivity Analysis Plan

	Ohiootivo	Outcome		Hymothosis	34.1.1.64.1.	
	Objective	Name	Type	Hypothesis	Method of Analysis	
1	Different analysis models	SSI / Reoperation	Binary	10% povidone- iodine will be more effective than CHG	Multi-level regression models with different correlation structures	

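### The as-treated sensitivity analyses are unadjusted comparisons by solution received: they can be biased if non-adherence is differential and prognostic, and one exposure rule depends on the outcome

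*Combined protocol and SAP*

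**What the plan says.** Section 5.2.4 item 4 states that as-treated "sensitivity analyses will be performed using the solution received as the independent variable". Participants with one surgery are classed by the solution used. Participants with several surgeries are classed in two ways: by the solution at the last operation before an outcome event, and by the solution used in most operations. Equal exposure to both solutions sends the participant back to the allocated group. Table 8 row 4 gives the model as multi-level regression on the as-treated group and names no covariates.

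Covariate adjustment is a separate analysis (item 3, Table 8 row 3). It lists Gustilo type, lower-extremity fracture, wound contamination, time to first debridement and other risk factors alongside treatment group, and it is not linked to item 4. No analysis in the document estimates an adherence effect from allocation.

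Section 4.6.5 lists, among the grounds on which a site may be withdrawn, fewer than 90% of eligible patients receiving the allocated solution and, separately, "differential adherence between study solutions". Data from a withdrawn site stay in the final analysis. Sections 5.2.1 and 5.2.2 make intention to treat the basis of the primary and secondary analyses, section 5.2.4 introduces the sensitivity analyses as ones that may be done, and section 5.2.2 defers final modelling to a separate SAP.

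**The concern.** Section 4.3.1 keeps patients who received the wrong solution in the trial in order to preserve the prognostic balance from randomisation. Item 4 regroups those patients by receipt and adjusts for nothing, so that balance is lost.

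The patients who move may not be typical. In section 1.7 some surgeons explained their preference by saying that "they felt the tissue toxicity was less with their chosen solution". Sections 4.6.2, 4.6.3 and 4.6.6 single out patients whose repeat operations may fall after a crossover as being at risk of the wrong solution. Section 4.8.4 describes staged debridement and related decisions as possible markers of injury severity and potential confounders. A link between deviation and prognosis is therefore plausible, although the documents do not show one.

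At stake is how a robustness check will be read. Confounding alone could make the as-treated result appear to support or to contradict the intention-to-treat result.

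The exposure rule is a separate problem. Classing a participant by the last operation before an outcome event makes exposure depend on the outcome, and gives no rule for a participant who has no event.

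**Working it through.** The documents give no figure for the as-treated analysis, so there is none to reproduce. The planning assumption is: "We have assumed that the povidone-iodine solution will achieve a 0.65 risk ratio for SSI with a 12.5% SSI baseline incidence". It gives 0.125 × 0.65 = 8.125% under povidone-iodine and an odds ratio of (0.08125/0.91875)/(0.125/0.875) = 0.62, which agrees with Table 5. Only the 12.5% is used in step 1.

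**1. No true effect.** Assumptions, not figures from the plan: each allocated arm has 12.5% risk; a fraction d of the arm receives the other solution; those patients have k times the risk of the rest of their arm. Non-deviators then have risk 0.125/(1 + d(k − 1)). Risk ratios are povidone-iodine over CHG.

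Take d = 10% under CHG, 2% under povidone-iodine, and k = 2:
- CHG arm: non-deviators 0.125/1.10 = 0.1136, deviators 0.2273.
- Povidone-iodine arm: non-deviators 0.125/1.02 = 0.1225, deviators 0.2451.
- Received povidone-iodine: (0.98 × 0.1225 + 0.10 × 0.2273)/1.08 = 0.1322.
- Received CHG: (0.90 × 0.1136 + 0.02 × 0.2451)/0.92 = 0.1165.
- As-treated risk ratio: 0.1322/0.1165 = 1.14.

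| Deviation, CHG / povidone-iodine | k | As-treated RR (true 1.00) |
|---|---|---|
| 10% / 2% | 2 | 1.14 |
| 2% / 10% | 2 | 0.88 |
| 5% / 2% | 2 | 1.05 |
| 10% / 2% | 1.5 | 1.07 |
| 10% / 10% | 2 | 1.00 |

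**2. Is k = 2 reasonable?** Section 1.1 reports reoperation in 13.2% of an earlier open-fracture trial overall, 18.0% in type III injuries and 29.8% with severe contamination. Relative to the overall rate these are 18.0/13.2 = 1.36 and 29.8/13.2 = 2.26. Applying such ratios to SSI in deviators is a further assumption; it only shows that k = 2 is not outlandish.

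**3. True risk ratio 0.65, one-way deviation.** Let 10% of CHG-allocated patients receive povidone-iodine, with none the other way, and let them have 2.26 times the average risk.
- Baseline risk of the remaining patients: (0.125 − 0.10 × 0.2825)/0.90 = 0.1075.
- Received povidone-iodine: (0.08125 + 0.10 × 0.2825 × 0.65)/1.10 = 0.0906.
- As-treated RR: 0.0906/0.1075 = 0.84.
- Intention-to-treat RR: 0.08125/(0.90 × 0.1075 + 0.10 × 0.2825 × 0.65) = 0.08125/0.1151 = 0.71.
- Complier RR: intention-to-treat risk difference −0.0339, divided by the 0.90 difference in receipt, = −0.0376; (0.1075 − 0.0376)/0.1075 = 0.65.

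At 1.36 times the average risk the as-treated RR is 0.70. With the deviation in the other direction, the as-treated RR is 0.60 at 1.36 and 0.50 at 2.26.

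**4. Limits of the complier estimate.** Suppose that, because of mixed exposure over several operations, the deviating patients in step 3 get only half the benefit (multiplier 0.825).
- CHG-arm risk: 0.90 × 0.1075 + 0.10 × 0.2825 × 0.825 = 0.1201.
- Complier difference: (0.08125 − 0.1201)/0.90 = −0.0431.
- Complier RR: (0.1075 − 0.0431)/0.1075 = 0.60, against a true 0.65. The as-treated RR in the same case is (0.08125 + 0.0233)/1.10/0.1075 = 0.88.

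**5. Interval method.** A percentile cluster bootstrap of the complier estimate was simulated with 1,400 patients, 12.5% risk, between-cluster variance 0.095, no effect and 5% deviation each way. Coverage of the nominal 95% interval was about 90% with 10 or 12 clusters.

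**The case against.** The case for leaving the plan alone is fair in several respects.

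- **Little depends on it.** The as-treated analysis is one of six optional sensitivity analyses behind an intention-to-treat primary analysis, no decision rule uses it, and a separate SAP is still to come. This stands, and it sets the weight of the point.
- **The bias is conditional.** Balanced deviation with similar prognosis gives none. Section 1.7 reports pre-trial preferences, not reasons for deviating within the trial, and does not mention wound severity. The doubled risk is assumed. This also stands.
- **The plan watches for the problem.** A reader might infer that 10% against 2% deviation is something the plan accepts because it lies within 90% adherence. The documents do not support that: section 4.6.5 makes differential adherence its own ground for withdrawing a site. Withdrawal is discretionary and the site's data are kept, so this limits the bias without removing it.
- **A complier analysis is not a clean substitute.** A reader might infer that it answers the same question without bias and should replace item 4. It does not answer the same question: it concerns patients who would receive whichever solution was allocated. It also needs monotonicity and no effect of allocation except through the coded exposure. Exclusion criterion 1, which removes patients who do not receive the allocated solution because of a contraindication, and mixed exposure over several operations strain these assumptions, as does consent after surgery. Step 4 shows that an error can remain.

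None of this justifies leaving the as-treated models unadjusted, when the covariates are already listed in item 3, or keeping an exposure rule that cannot be applied to participants without an event.

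**Conclusion.** The point holds as a minor one. Item 4 and Table 8 row 4 specify an unadjusted, non-randomised comparison. Under no true effect, and on the stated assumptions, its risk ratio could be about 1.14 or 0.88 at 10% against 2% deviation with doubled risk in deviators, 1.07 at 1.5 times the risk, and 1.00 when deviation is balanced with similar prognosis. The realised adherence and the prognosis of deviators are not known from the documents, so these figures show how large the bias could be and do not predict it. The primary and secondary intention-to-treat results are not affected. The rule based on the last operation before an outcome event needs correcting whatever the adherence turns out to be.

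**What to change.** In the separate SAP:

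1. Adjust the as-treated models for the item 3 risk factors (Gustilo type, limb, contamination and the others), and label the results as non-randomised comparisons in which residual confounding may remain.
2. Code solution received by a rule that does not use the outcome and applies equally to participants with and without an event.
3. As a supportive addition, report a complier-average effect with allocation as the instrument: the intention-to-treat risk difference divided by the between-arm difference in the proportion coded as receiving povidone-iodine. Give a relative form as well, since section 5.2.1 calls for relative measures with "corresponding two-sided 95% confidence intervals". State the population it concerns, the two assumptions, and that exclusion criterion 1 and mixed exposure strain them. Use a small-sample interval method suited to 10 to 12 clusters; a plain percentile cluster bootstrap is too narrow.

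The cost is wording and one extra analysis on data already collected. The complier interval is wider than the intention-to-treat interval by about 1/0.9 = 1.11 at 5% deviation each way (0.95 − 0.05 = 0.90), and there is no gain in power.

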## 1.5 Why Iodophor Skin Preparations May Reduce Open Fracture SSI

The only surgical skin preparation effectiveness data available for open fracture management come from the FLOW trial. Secondary multivariable analyses of 2,447 patients with open fractures found that when compared to chlorhexidine solutions, iodophor-based skin antiseptic preparation solutions could be protective against complications (Adjusted Hazard Ratio 0.88, 95% CI: 0.69–1.12). However, the wide CI suggests iodophor solutions may reduce the odds of infection by as much as 31% or increase it by as much as 12%, leaving its superiority as a fracture care surgical preparation solution unresolved.

There are several chemical properties to suggest povidone-iodine may be more effective than CHG at preventing open fracture SSI. Firstly, povidone-iodine has a broader spectrum of antimicrobial activity. Secondly, many open fracture patients require repeat surgical debridement and therefore, these patients will receive multiple exposures to the pre-operative antiseptic solution. Extended use of povidone-iodine has not been associated with the selection of resistant bacterial strains, whereas bacterial resistance to chlorhexidine has been documented. He methods for detecting CHG resistance are challenging and its clinical significance remains uncertain, these early observations heighten interest in establishing the comparative effectiveness of iodophors versus CHG.

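### The first as-treated rule names no index surgery for multi-surgery participants without an event, and the natural way to complete it makes exposure depend on the outcome

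*Combined protocol and SAP*

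**What the plan says.** Section 5.2.4 item 4 plans as-treated sensitivity analyses for SSI and reoperation. It gives four rules.

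- **One surgery:** "For participants that were treated in a single open fracture surgery, they will be analyzed using the antiseptic solution received". No event is needed.
- **Several surgeries, first analysis:** "First, the antiseptic solution used in their last surgery prior to a study outcome event will define their study treatment".
- **Several surgeries, second analysis:** treatment is "the antiseptic solution received in the majority of their" fracture surgeries. No event is needed.
- **Equal exposure to both solutions:** these participants "will be analyzed within their originally allocated treatment group". The text does not say whether this covers the first analysis, the second, or both.

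Table 8, row 4, refers only to the as-treated group and adds no definition. Sections 4.8.1 and 4.8.2 count SSI and reoperation from the fracture onward, so an event can come before a later planned surgery. Section 1.5 expects repeated exposure to be common: "many open fracture patients require repeat surgical debridement and therefore, these patients will receive multiple exposures to the pre-operative antiseptic solution". Section 4.6.2 recognises that a planned repeat surgery may fall in a period using the other solution. Section 4.6.5 lists "differential adherence between study solutions" among the reasons a site may be withdrawn.

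**The concern.** The first rule locates the exposure by reference to the outcome. Taken literally, it classifies multi-surgery participants with an event and leaves the others without a treatment group, so event risks cannot be compared. An analyst must complete the rule, and the document does not say how.

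The obvious completion uses the last surgery of all for participants without an event. Cases are then labelled on a sequence of surgeries cut off at the event, and non-cases on the full sequence. Non-cases have more opportunities to be relabelled by a wrong solution at a later surgery. If those errors are commoner with one solution, the label is associated with the outcome even when the solutions are equally effective.

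At stake is the value of this check. It is meant to show whether the result holds up once incorrect solution use is taken into account, and it would be least reliable when adherence differs between solutions. Two analysts could also code it differently, possibly after seeing outcomes.

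**Working it through.** **1. The plan's own figures.** Section 5.1 says: "We have assumed that the povidone-iodine solution will achieve a 0.65 risk ratio for SSI with a 12.5% SSI baseline incidence".

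- Povidone-iodine risk = 0.125 × 0.65 = 0.08125.
- Absolute difference = 0.125 − 0.08125 = 0.04375, the stated reduction of about 4%.
- Odds ratio = (0.08125/0.91875)/(0.125/0.875) = 0.619, the 0.62 in Table 5.

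The inputs reproduce.

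**2. Share without an event.**

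- SSI, trial-wide: 1 − (0.125 + 0.08125)/2 = 0.897.
- Reoperation, 13% baseline and the same risk ratio: 1 − (0.13 + 0.0845)/2 = 0.893; with no effect, 0.87.
- Multi-surgery participants: no rate is given. As a proxy, section 1.1 reports reoperation rates of 18.0% in Type III injuries and 29.8% with severe contamination, so 82% and 70% without an event. I take 70-90% as an assumed range.

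**3. Does another rule fill the gap?** The single-surgery and majority rules do not apply to the first analysis. The tie rule covers only equal exposure. A participant with three surgeries, two with one solution and one with the other, and no event stays undefined. A participant with one surgery of each and an event meets both the first rule and the tie rule, which may disagree.

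**4. Bias of the natural completion with no treatment effect.** All inputs here are assumptions:

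- m = share of participants with more than one surgery;
- wrong solution at the first surgery = 5% in both groups;
- L = wrong solution at the last surgery, in the allocated povidone-iodine group (5% under CHG);
- e = share of multi-surgery events occurring before the later surgery;
- equal allocation, and equal event risk with one or several surgeries.

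Wrong-label share in the povidone-iodine group:

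- non-cases: w0 = (1 − m)(0.05) + mL
- cases: w1 = (1 − m)(0.05) + m[0.05e + (1 − e)L]

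In the CHG group it is 0.05 for both. Then

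OR = [(1.05 − w1)/(0.95 + w1)] / [(1.05 − w0)/(0.95 + w0)]

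| L | m | e | w0 | w1 | OR |
|---|---|---|---|---|---|
| 15% | 0.30 | 0.20 | 0.080 | 0.074 | 1.01 |
| 15% | 0.70 | 0.40 | 0.120 | 0.092 | 1.06 |
| 25% | 0.30 | 0.20 | 0.110 | 0.098 | 1.02 |
| 25% | 0.70 | 0.40 | 0.190 | 0.134 | 1.12 |

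The last row is (0.916/1.084)/(0.860/1.140) = 1.12. Exchanging the groups gives 1/1.12 = 0.89, a spurious benefit in the hypothesised direction. With equal wrong-solution rates, the two labels are equally frequent among cases and among non-cases, so OR = 1.00.

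**5. Scale.** With 700 per group, event risk 0.103 and patients treated as independent, the standard error of the log odds ratio is √[2/(700 × 0.103) + 2/(700 × 0.897)] = 0.176. The largest bias is ln(1.12)/0.176 = 0.113/0.176, about 0.6 standard errors. The upper 15% case is ln(1.06)/0.176, about 0.3.

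**6. Check under other assumptions.** A simulation took multi-surgery participants only, with two to four surgeries, 18% event risk and 30% or 60% of events before the last planned surgery. With wrong-solution use at later surgeries of 5% versus 15%, 2% versus 20% and 5% versus 25% (povidone-iodine versus CHG), the null odds ratio was 0.87-0.96. With equal use it was 1.00. Indexing everyone on the last planned surgery gave 0.996-1.007 throughout.

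**The case against.** The best defence is that the gap matters for few people and little is at stake. Much of this stands.

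- **Who is affected.** A participant given one solution throughout gets the same label under any completion. A reader might infer that every event-free multi-surgery participant is effectively lost: if half of the 1,540 had several surgeries, 0.5 × 1,540 × 0.897 = about 690. The documents do not support that. They require the same solution at all planned surgeries, monitor compliance and set a 90% threshold. In the simulated scenarios, 17-31% of multi-surgery participants had mixed exposure, which would make about 117-214 of the 690. These shares are assumed, and the tie rule might settle some of the cases.
- **The 90% figure.** It is tempting to apply it to multi-surgery participants. It is a trial-wide planning figure, and these participants are probably more severely injured.
- **Differential adherence.** Section 4.6.5 names it as a ground for withdrawing a site. It does not predict it.
- **Status.** The opening of 5.2.4 presents the sensitivity analyses as optional, the majority-rule analysis can classify participants without events, and sections 5.2.1 and 5.2.2 promise a separate analysis plan.

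What does not stand is that this is only missing detail. The rule as written ties exposure to the outcome and cannot be run literally. Participants with mixed exposure are the very ones a multi-surgery rule exists to classify. The promised plan is the right place for a correction but does not itself provide one.

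**Conclusion.** The point holds in a limited form. The first as-treated rule is undefined for multi-surgery participants without an event, who are the majority, and its natural completion makes the exposure window depend on the outcome. The resulting bias is nil when wrong-solution use at later surgeries is equal between solutions and small to modest otherwise: at most about 12% on the odds ratio, or 0.6 standard errors, in the most unfavourable scenario tabulated. That scenario combines 25% versus 5% wrong-solution use, 70% of participants with several surgeries and 40% of their events before the later surgery. None of these comes from the documents.

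A reader might infer that the trial's main conclusions are at risk. They are not: the primary and secondary analyses follow allocation and do not use this rule. The correction should be made because the rule cannot be applied as written and the remedy is cheap.

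**What to change.** In 5.2.4 item 4, or in the separate analysis plan before outcomes are examined, replace the first rule with a definition that applies identically whether or not an event occurs. Preferably: solution received is a time-varying exposure, updated at each planned open fracture surgery, and event risk is compared by solution among participants still event-free at that surgery. Participants with one surgery fit the same definition.

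A classification by first surgery can be added as a simple supplementary version. It should not be the main replacement, because it discards the later surgeries, where carry-over between periods is most likely and which this analysis is meant to examine.

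State also whether the tie rule applies to the first analysis, the second, or both. Under the time-varying version there is no tie to break, so it would naturally be confined to the majority analysis.

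The cost is a few sentences and a little more analysis work. Item 4 already requires incorrect solution use to be reported by procedure, and section 4.8.4 collects event dates. The date of each planned surgery is also needed; I assume that the surgical case report forms hold it.
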